### **Primary Endpoint**

- The primary safety endpoint is the frequency of grade 3 or 4 AEs considered to be possibly, probably, or definitely related to the treatment regimen.

**Phase IIa.** The Phase IIa component of the trial is designed to be a single arm trial of IFN $\alpha$  (at MTD, if reached, otherwise at 20 MU/M) + rintatolimod along with the best available standard of care. Using each patient's baseline nasopharyngeal viral load, we will evaluate to what extent the study regimen reduces viral load relative historical institutional benchmarks. The sample size will be n=10.

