### 19.2.2 Efficacy

In order to compare the AUC between rintatolimod versus historical institutional benchmarks we will use the highly efficient approach proposed by Chandrasekhar et al (48). Ct values measured at baseline (Day 0), Days 3, 7 and 14 will be used to measure the AUC using a standard trapezoidal rule where the AUC for the  $i$ th subject in group  $k$  ( $k=1$  for rintatolimod and  $k=2$  for control) as  $AUC_{jk} = \sum_{i=1}^m c_j Y_{ijk}$  where  $t_1 = 0, t_2 = 3, t_3 = 7, t_4 = 14, t_5 = 30$ ,  $m = 5$ , the  $Y_{ijk}$ 's denote the corresponding Ct values per subject at the respective time points and

$$c_j = \begin{cases} \frac{t_{j+1} - t_j}{2}, & j = 1 \\ \frac{t_j - t_{j-1}}{2}, & j = m \\ \frac{t_{j+1} - t_{j-1}}{2}, & \text{otherwise} \end{cases}$$

If a Ct value is  $>40$  it will be considered right censored for the purpose of this analysis, which corresponds to a non-detectable level. We can re-express this formulation using a linear mixed model with details given exactly as in Chandrasekhar et al. (48). A large AUC value for a respective subject is a measure of treatment efficacy as compared to a subject with a lower AUC

Roswell Park Protocol No.: I-659920

value. The primary test of efficacy will be H0:  $AUC=130$  (log2 copies) x day versus H1:  $AUC>130$  (log2 copies) x day.

The secondary clinical efficacy endpoints of (i) progression of infection requiring hospitalization in patients who were not inpatients at study entry; (ii) respiratory failure requiring mechanical ventilation; and (iii) death within 30 days will be compared using Fisher's exact test. Time to a Ct value of non-detectable will be examined using an exact discrete time-to-event Cox model. The analysis of correlative endpoints will be primarily descriptive and graphical in nature.

The primary test of efficacy will be one-sided and tested at level alpha=0.05. All additional tests will be two-sided and tested at level alpha=0.05.

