### **19.3 Sample Size Justification**

The sample size was based on preliminary data gathered at Roswell Park on patients and employees. The values were similar between the two study groups. The Ct values collected at baseline for n=20 patients and employees had an average of 24.1 log2 copies with a standard deviation of 6.5. The standard deviations after baseline was approximately 4.5 as the Ct values increased. The preliminary estimate for the AUC based on our pilot data is 130 (log2 copies) x day, which is the basis for our null hypothesis. The between time point correlation was estimated to be approximately rho=0.3. Given n=10 subjects we will be able to detect and increase in the AUC to an average of 144 (log2 copies) x day (efficacy) or greater than our assumed institutional benchmark of 130 (log2 copies) x day at power=0.80 and alpha=0.05(one-sided). We simplified this calculation assuming no censoring, which will be accounted for in the final analysis and assumed a compound symmetry covariance structure with the correlation estimate described above.

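### With the SDs and correlation in Section 19.3, n = 10 gives about 22% power (Days 0–14) or 11% (Days 0–30) for a 14-unit AUC increase, not the stated 80%

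*Combined protocol and SAP*

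**What the plan says.** Phase IIa is a single-arm comparison with a fixed institutional benchmark. Section 19.1 sets its size: "The sample size will be n=10". Section 19.2.2 defines the endpoint as a trapezoidal AUC of Ct over days and says "The primary test of efficacy will be one-sided and tested at level alpha=0.05".

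Section 19.3 gives the only justification for n = 10:

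- Benchmark: "The preliminary estimate for the AUC based on our pilot data is 130 (log2 copies) x day".
- Claim: "Given n=10 subjects we will be able to detect and increase in the AUC to an average of 144 (log2 copies) x day", "at power=0.80 and alpha=0.05(one-sided").
- Variability: baseline Ct "had an average of 24.1 log2 copies with a standard deviation of 6.5", with an SD of about 4.5 at later visits.
- Correlation: "The between time point correlation was estimated to be approximately rho=0.3".
- Structure: the authors "assumed a compound symmetry covariance structure with the correlation estimate described above", and ignored censoring for this calculation.

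Section 19.2.2 gives two time grids. Its text uses Days 0, 3, 7 and 14; its formula has five points ending at Day 30.

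**The concern.** An AUC over 14 or 30 days multiplies each Ct value by several days, so SDs of 4.5 to 6.5 cycles produce a large SD for the AUC. A 14-unit difference over 14 days is one cycle on average. Ten patients with SDs of this size and a positive correlation between visits cannot plausibly detect that with 80% power.

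The stated power is the whole case for n = 10 on the primary Phase IIa efficacy endpoint. If it is wrong, a trial with a properly set null would usually miss a true 14-unit effect. A negative result could then be taken as evidence against antiviral activity because the protocol claims 80% power. Section 2.6 says a reduction in nasopharyngeal viral load is to support a larger randomized trial, so a false negative would matter.

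**Working it through.** **Inputs.** From 19.3: SDs 6.5 (baseline) and 4.5 (later), rho = 0.3 for every pair of visits, no censoring, n = 10, difference 144 − 130 = 14, one-sided alpha 0.05. From 19.2.2: the trapezoid weights.

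**What the stated 80% requires.** For a one-sample test, the noncentrality is 14 × √10 / SD(AUC) = 44.27 / SD(AUC). Power of 80% needs this to equal 2.697 (noncentral t, 9 df) or 1.645 + 0.842 = 2.486 (normal). So SD(AUC) must be 44.27/2.697 = 16.4 (t) or 44.27/2.486 = 17.8 (normal).

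**What the inputs give.** With a_j = weight × SD, compound symmetry gives

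Var(AUC) = Σa² + rho × [(Σa)² − Σa²].

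*Days 0, 3, 7, 14.* Weights 1.5, 3.5, 5.5, 3.5, so a = 9.75, 15.75, 24.75, 15.75. Σa² = 1203.75 and Σa = 66. Var = 1203.75 + 0.3 × (4356 − 1203.75) = 2149.4, so SD = 46.4.

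*Days 0, 3, 7, 14, 30.* Weights 1.5, 3.5, 5.5, 11.5, 8, so a = 9.75, 15.75, 24.75, 51.75, 36. Σa² = 4929.75 and Σa = 138. Var = 4929.75 + 0.3 × (19044 − 4929.75) = 9164.0, so SD = 95.7.

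| | Days 0–14 | Days 0–30 |
|---|---|---|
| SD(AUC) | 46.4 | 95.7 |
| Noncentrality for 14, n = 10 | 0.955 | 0.462 |
| Power, t | 22.3% | 11.2% |
| Power, normal | 24.5% | 11.9% |
| Increase detectable at 80%, n = 10, t | 39.5 | 81.6 |
| Same, normal | 36.5 | 75.3 |
| n for 80% power at 14, t | 70 | 291 |

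**Sensitivity.** The detectable increase at n = 10 (t, 80% power) stays well above 14 under other readings of the day-based AUC:

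- rho = 0 on Days 0–14: 29.6 (power for 14: 32%).
- All SDs 4.5 on Days 0–14: 38.1 (power 23%).
- Days 0–7 only: 21.8 (power 48%).
- Baseline-subtracted AUC, Days 0–14: 63.7.

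A two-sided test or a two-group comparison with 10 per group lowers power further on both of the plan's grids.

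**Scale of the benchmark.** A Ct flat at the baseline mean of 24.1 already gives 24.1 × 14 = 337 over 14 days or 24.1 × 30 = 723 over 30 days. A value of 130 would mean an average Ct of 130/14 = 9.3 or 130/30 = 4.3. So 130 is not on the day scale either.

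**The case against.** The strongest counter-argument is that one slip in scale may explain both 130 and 14. If the five visits are treated as one unit apart, the weights are 0.5, 1, 1, 1, 0.5 and SD(AUC) is 12.7. Then 130 means an average Ct of 130/4 = 32.5, which is plausible. A two-group normal calculation with 10 per group then has a detectable difference of 14.1 and power of 79% for 14 (76% by t). Remnants of a two-group design do survive: Section 19.2.2 indexes a control group and Section 19.1 mentions randomization. On this reading 14 units is 14/4 = 3.5 cycles on average, or 49 Ct x day over 14 days, and n = 10 in a one-sample test would have about 92% power for that (t).

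This does not support Section 19.3 as written. It contradicts the day-based weights, the units and the single arm. With unit spacing and the planned one-sample test, power is 94–97%, again not 80%. Unit spacing with a common SD of 6.5 in one sample gives 75–81%, but contradicts the stated later SD of 4.5. Either route is inference about how the figure arose.

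Three parts of the objection stand. First, 22% and 11% are not the chance of rejecting the null as written: on the day scale almost any patient exceeds 130, so that test would nearly always reject. Second, 14 may be on the wrong scale too, so the documents do not settle whether the trial is insensitive to the effect the authors had in mind. Third, the Day 30 figure carries less weight, because the Main Cohort calendar schedules swabs only to Day 14.

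**Conclusion.** The concern holds. The claim of 80% power for 144 versus 130 with n = 10 does not follow from the plan's own inputs. On the Days 0–14 grid, power for a 14-unit increase is 22% (t) or 25% (normal); on the Days 0–30 grid it is 11–12%. The SD(AUC) implied by the inputs is about 2.8 times (46.4/16.4) or 5.8 times (95.7/16.4) what the claim needs.

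The result rests on the stated SDs, rho = 0.3, compound symmetry, no censoring, complete data, the day-based weights and a one-sample one-sided test. The choice of t or normal moves it by about two points at most.

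Correcting 130 alone would not repair the claim, because the power for a given difference depends on SD(AUC) and not on the null value. If the null is corrected and the difference stays at 14 on the Days 0–14 scale, a true effect of that size would be missed about 78% of the time.

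**What to change.** Keep n = 10 and rewrite Section 19.3 in this order:

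1. Fix one time grid in Section 19.2.2. Days 0, 3, 7 and 14 match its text and the Main Cohort calendar.
2. Recompute the benchmark and the alternative from the pilot data on that grid.
3. State SD(AUC) (46.4 with the present inputs) and the test used for the power calculation.
4. Restate the sensitivity: with n = 10 and one-sided alpha 0.05, power is 80% for an increase of about 40 Ct x day over Days 0–14 (39.5/14 = 2.8 cycles on average), and about 22% for an increase of 14 on the same scale. If step 2 shows that 14 was meant on another scale, give the power for the rescaled alternative instead.

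The cost is a change of protocol and SAP wording, with no extra patients or visits. The price is a less favourable statement of what ten patients can show for a 14-unit increase on the day scale.

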### **Primary Endpoint**

- Evaluate kinetics of viral load expressed as Ct values in nasopharyngeal swab samples over time measured at baseline (day 0), Days 3 (last day of treatment), 7, and 14 (40). The primary endpoint will be the area under the Ct curve (AUC).

The primary Phase IIa safety endpoint is the frequency of grade 3 or 4 AEs considered to be probably or definitely related to the treatment regimen.

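### The primary AUC is built from Ct values, but its benchmark of 130 and target of 144 are given in log2 copies, and 130 cannot be a Day 0–14 Ct area

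*Combined protocol and SAP*

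**What the plan says.** Section 19.1, under the Phase IIa primary endpoint, names the variable: "The primary endpoint will be the area under the Ct curve (AUC"). Section 19.2.2 builds the area by the trapezoidal rule from Y values that "denote the corresponding Ct values per subject at the respective time points". It treats a Ct above 40 as right-censored, "which corresponds to a non-detectable level", and it states the direction: "A large AUC value for a respective subject is a measure of treatment efficacy". It then sets a one-sided test at 0.05 of H0: AUC = 130 against H1: AUC > 130, both in (log2 copies) x day.

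Section 19.3 gives the source of the constants. The baseline Ct values "had an average of 24.1 log2 copies with a standard deviation of 6.5". The benchmark is described thus: "The preliminary estimate for the AUC based on our pilot data is 130 (log2 copies) x day". The alternative is in the same unit and marked as efficacy: the trial is said to be able to "detect and increase in the AUC to an average of 144 (log2 copies) x day (efficacy"), with n = 10, power 0.80 and one-sided alpha 0.05. The same section says that Ct values increased after baseline.

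**The concern.** Ct and log2 copies run in opposite directions: the more RNA in the sample, the fewer cycles are needed to detect it. The endpoint is defined on one scale and its hypothesis constants are labelled on the other. On the label alone, a move from 130 to 144 is more virus, yet the plan calls it efficacy.

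This is the only primary efficacy test. It is one-sided, in a single arm of 10 patients, against a fixed number. Such a test means something only if the variable, the unit, the null value and the direction agree. If the null value is not on the scale of the data, a positive result says nothing about the regimen.

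**Working it through.** **Inputs**
- Days 0, 3, 7 and 14 and the trapezoid weights: section 19.2.2.
- Baseline mean 24.1, SD 6.5 at baseline and 4.5 afterwards, correlation 0.3 with compound symmetry, n = 10, null 130, alternative 144: section 19.3.

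**1. Weights.** For Days 0, 3, 7 and 14 they are 3/2 = 1.5, 7/2 = 3.5, 11/2 = 5.5 and 7/2 = 3.5, summing to 14.

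**2. SD of the area.** Weight times SD gives 9.75, 15.75, 24.75 and 15.75. The sum is 66.0 and the sum of squares is 1203.75.
- Variance = 0.7 × 1203.75 + 0.3 × 66.0² = 842.6 + 1306.8 = 2149.4
- SD = 46.4
- SE at n = 10 is 46.36/√10 = 14.66

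**3. The plan's power figure.** The shift of 14 is 14/14.66 = 0.95 SE. One-sided power is 0.22 by the noncentral t (0.25 by the normal approximation), not 0.80. Of the variants tried with the stated SDs, only an unweighted sum of five Ct values reproduces 0.80:
- Variance = 0.7 × 123.25 + 0.3 × 24.5² = 266.35
- SD = 16.3, power 0.804 (t)
- On that scale 130 is a mean Ct of 130/5 = 26.0 and 144 is 144/5 = 28.8

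This sum is not the plan's AUC. It shows only that a Ct-based origin for 130 and 144 is plausible.

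**4. Can 130 be a Ct area over Days 0 to 14?**
- A flat Ct of 24.1 gives 14 × 24.1 = 337.4. Ct rose after baseline in the pilot, so the pilot's mean area should be at least this.
- An area of 130 implies a mean Ct of 130/14 = 9.3.
- The formula in section 19.2.2 also lists a fifth point at Day 30. Over 30 days the flat path gives 30 × 24.1 = 723, and 130 implies a mean Ct of 130/30 = 4.3. The mismatch grows.

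**5. What the test does if 130 is kept.**
- A group with flat Ct 24.1 lies (337.4 − 130)/14.66 = 14.1 SE above the null. Rejection is practically certain.
- The rejection boundary (t with 9 df, 1.833) is 130 + 1.833 × 14.66 = 156.9, a mean Ct of 156.9/14 = 11.2. A group with a mean Ct well above that rejects, whatever the treatment did.
- With SD 6.5 at every visit the area SD is 64.6, and the distance is 207.4/(64.58/√10) = 10.2 SE. The conclusion does not depend on the exact SD.

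**6. Direction.** Four statements are on the Ct scale: the endpoint definition, the definition of Y, the efficacy sentence, and right-censoring above 40 (on a copies scale a non-detect would be left-censored). Section 19.3 attaches the words log2 copies to the Ct values themselves. Only the unit words disagree.

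**The case against.** A reader might infer that the label is real, that 130 was derived on a copies-like scale, and that the one-sided test therefore looks for more virus and rewards harm. The argument has some force, because 130 does fall in the range of areas of 40 − Ct over Days 0 to 14. A path of 24.1, 27.5, 31.5, 35.5 gives 1.5 × 15.9 + 3.5 × 12.5 + 5.5 × 8.5 + 3.5 × 4.5 = 130.1.

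The documents do not support that reading:
- The post-baseline values in that path are assumed; only 24.1 is in the plan. Other paths from the same baseline give 223 (flat), 124 (28, 32, 36) or 81 (30, 36, 40), so a match can be had by choosing the path.
- The power on that scale is 0.22, as in step 3, whereas a sum of Ct values comes close to the stated 0.80.
- Section 19.3 marks the higher value, 144, as efficacy, which is wrong on a copies scale and right on a Ct scale.
- The data to be analysed are Ct in any case, so the upper tail of the planned test is the benefit direction.

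From the other side, one may say that this is only a wrong word. That is fair for the direction of the test. It does not cover the size of 130: striking out the unit leaves a benchmark that the defined Ct area would exceed almost surely. What stands is that the origin of 130 is unknown and has to be established.

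**Conclusion.** The concern holds as an inconsistency of unit and scale. The baseline, null and alternative carry a unit of opposite sign to the endpoint, and 130 is less than half of the 337 that a flat Ct of 24.1 gives over 14 days. Used as written, the test would reject with probability about 1 with or without a treatment effect. It does not hold that the planned test is in the wrong tail.

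The probability rests on the plan's SDs and correlation, no censoring (as in section 19.3), a mean Ct of at least about 24 in the trial patients, and the Day 0–14 trapezoid. The Day 0–30 window makes the gap larger. How the pilot produced 130 cannot be told from the documents.

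**What to change.** Before analysis, check how the pilot AUC was computed: the variable, the weights and the time window. Then, in sections 19.2.2 and 19.3:
- state the baseline mean, the null and the alternative in Ct cycles x day, computed with the same trapezoid and the same days as the endpoint;
- keep H1 as AUC greater than the benchmark on that scale;
- recompute the power with those values, since the trapezoid does not give 0.80 for a difference of 14.

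If the pilot constants turn out to be on a copies-like scale, convert them. On a 40 − Ct scale over 14 days, for example, the null would become 14 × 40 − 130 = 430 Ct cycles x day, and the alternative would have to be set above it. Do not reverse H1: applied to the plan's Ct area, that would create the wrong-tail error that the text now avoids.

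The cost is one look at existing pilot data and a wording change in the statistical plan. No visit or sample is added. The corrected power may call for a separate decision on sample size.

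### The primary test sets a right-censored AUC against a pilot benchmark of 130 whose handling of non-detectable swabs is not stated

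*Combined protocol and SAP*

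**What the plan says.** Section 19.1 describes Phase IIa as follows: it "is designed to be a single arm trial of" IFNα plus rintatolimod with standard of care, n=10. Its primary efficacy endpoint is the area under the Ct curve.

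Section 19.2.2 computes the AUC by the trapezoidal rule. For a Ct above 40, "it will be considered right censored for the purpose of this analysis, which corresponds to a non-detectable level". The model is a linear mixed model taken from the cited method, which reference 48 identifies as likelihood inference on a mean AUC with limits of detection. A larger AUC counts as efficacy. The test is H0: AUC = 130 against H1: AUC > 130, one-sided at 0.05.

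Section 19.3 gives the source of the null value: "The preliminary estimate for the AUC based on our pilot data is 130 (log2 copies) x day, which is the basis for our null hypothesis". It claims 80% power with n=10 for an increase to 144. It then says: "We simplified this calculation assuming no censoring, which will be accounted for in the final analysis". The same sentence goes on to the covariance structure and correlation assumed.

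Nothing in 19.2.2 or 19.3 says whether the pilot had values above 40, how any were treated, or whether 130 will be recomputed by the final method.

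**The concern.** A right-censored likelihood lets a non-detectable swab stand for a value somewhere above 40. The fitted visit mean is therefore higher than one computed with that swab set to 40 or left out. If the trial AUC is built the first way and the benchmark the second, the same swabs give a larger AUC on the trial side, and larger is read as success. The bias would sit in the primary test, always favour the drug, and grow with the share of patients who clear. With a single arm there is no concurrent group analysed the same way to cancel it.

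Non-detects are to be expected. Time to a non-detectable Ct is a secondary endpoint (19.1), and the text with Figure 1 reports that the first patient cleared virus by Day 3.

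**Working it through.** **Inputs.** From 19.3: baseline Ct mean 24.1 and SD 6.5, post-baseline SD about 4.5, correlation 0.3 with compound symmetry, n=10, one-sided alpha 0.05, AUC 130 against 144. From 19.2.2: sampling Days 0, 3, 7 and 14, which give trapezoid weights 1.5, 3.5, 5.5 and 3.5 (sum 14). The formula there also lists Day 30; the figures below use the four days named in the text. The post-baseline mean Ct by visit is not given, so the mean paths are assumptions.

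**The plan's own figure.** The products weight × SD are 9.75, 15.75, 24.75 and 15.75. Their sum of squares is 1203.75 and their sum is 66.

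- SD(AUC) = √(0.7 × 1203.75 + 0.3 × 66²) = √(842.6 + 1306.8) = 46.4.
- For a difference of 14 with n=10, one-sided power by noncentral t is 0.22, not 0.80. Power of 0.80 needs an SD(AUC) of about 16.4.
- With Day 30 included, SD(AUC) is 95.7 and power 0.11.

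**The scale of 130.** A flat Ct of 24.1 gives 24.1 × 14 = 337. Conversely, 130/14 = 9.3 would be the mean Ct. With a standard error of 46.4/√10 = 14.7, a flat Ct of 24.1 lies (337 − 130)/14.7 ≈ 14 standard errors above the null. The test as written would reject with probability about 1, with or without censoring.

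**Effect of the non-detect rule.** Take a benchmark on the trapezoid scale, unchanged kinetics, and latent normal Ct values with mean μ and SD s at each visit. Let z = (40 − μ)/s. The censored likelihood targets μ. The alternatives fall short of μ by:

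- capped at 40: s[φ(z) − z(1 − Φ(z))];
- dropped: sφ(z)/Φ(z).

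The bias is the weighted sum over visits. Example, capped, path 24.1, 28, 33, 38: at Day 14, z = 0.444 and the shortfall is 4.5 × (0.361 − 0.444 × 0.328) = 0.97. The four shortfalls are 0.015, 0.005, 0.116 and 0.970. Weighted, they are 0.02 + 0.02 + 0.64 + 3.39 = 4.1.

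Type I error comes from the noncentral t with 9 df and noncentrality bias/14.7.

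| Assumed mean Ct, Days 0/3/7/14 | Non-detectable at Day 14 | Bias if capped | Type I error | Bias if dropped | Type I error |
|---|---|---|---|---|---|
| 24.1/26/28/30 | 1% | 0.1 | 5% | 1.1 | 6% |
| 24.1/27/31/35 | 13% | 1.3 | 6% | 5.6 | 10% |
| 24.1/28/33/38 | 33% | 4.1 | 8% | 12.0 | 19% |
| 24.1/28/34/40 | 50% | 7.4 | 12% | 17.4 | 29% |
| 24.1/30/37/43 | 75% | 16.7 | 28% | 31.2 | 63% |

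If the pilot had no non-detects, or was analysed by the same censored likelihood, the bias is 0 and the type I error 5%.

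These rates are approximate. They use the uncensored SD and a one-sample t-test in place of a fitted censored mixed model, and they treat the benchmark as a fixed number.

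**The case against.** A reader might infer from 19.3 that 130 itself was computed with censoring ignored, so that the two sides of the test are known to differ. The text does not support that. The sentence follows the power statement and continues with compound symmetry and the correlation, which a power calculation needs and an average of pilot AUCs does not. A no-censoring power calculation on its own affects precision and power, not false efficacy. Section 19.2.2 also introduces the limit-of-detection method for the comparison with institutional benchmarks, indexes a control group, and does not confine the rule for Ct above 40 to treated patients. A mismatch is therefore possible, not documented.

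The bias may also be small. Section 2.6 reports viral load persisting for several weeks in some immunocompromised patients, and at 13% or fewer non-detects capping costs almost nothing. Of the variants tried, only an unweighted sum of five Ct values reproduces the stated power (SD 16.3, power 0.804). If 130 were such a sum, the mean post-baseline Ct would be (130 − 24.1)/4 = 26.5, where about 0.1% of values exceed 40. That sum is not the AUC defined in 19.2.2, however.

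Nor do the tabulated rates describe the written test against 130, where the scale discrepancy dominates. For the same reason the biases should not be set against the planned difference of 14.

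All of this stands, and it makes the bias conditional. It does not remove the gap. Once 130 is put on the trapezoid scale, someone must decide how pilot non-detects enter, and the plan does not say.

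**Conclusion.** The concern holds in conditional form. The plan fixes a censored-likelihood analysis for the trial and a pilot number for the null, and does not tie the second to the first. If pilot non-detects were capped, the bias toward efficacy is about 0 to 17 AUC units, with type I error about 5% to 28%. If they were dropped, it is about 1 to 31 units and about 6% to 63%. If there were none, or the same likelihood was used, it is zero. The ranges rest on assumed mean paths with about 1% to 75% non-detectable at Day 14, Days 0–14 weights, SDs 6.5 and 4.5, correlation 0.3 and n=10.

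The larger discrepancy is that 130 cannot come from the trapezoid AUC in 19.2.2 with the Ct values in 19.3. Both must be corrected together, because re-deriving the benchmark under a different non-detect rule would leave this bias in place.

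**What to change.** Before Phase IIa opens:

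- In 19.3, state how many pilot values exceeded 40 and how they were handled.
- Re-estimate the benchmark from the individual pilot Ct values with the same visits, trapezoid weights and right-censored model as the trial analysis. Settle first whether Day 30 belongs in the AUC.
- Replace 130 with that value in 19.2.2 and 19.3.
- Restate the detectable difference or the power for n=10 with censoring included.

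Capping every value at 40 on both sides is not recommended: it would put single-value substitution in place of the planned likelihood.

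The cost is SAP wording and one re-analysis of existing data. The benchmark and the stated power may become materially less favourable.
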